**ID: 2019028**

**NCT number: not yet assigned**

**2019/10/1**

## **Study protocol**

Ten individuals (aged 20–30) will be selected to participate in the study. Selected patients should agree to participate in this study by signing a written consent stating, approved by the Fujian Medical University Ethics Committee (Code 2019-28), that they had been informed of the study. The selection criteria for the participants are as follows: (1)with one mandibular first molar requiring crown restoration that have undergone root canal treatment; (2)with complete permanent dentition; (3) without carious lesions, abrasions, attrition, erosions or any kind of tooth defects; (4) without any kind of restorations in occlusal surfaces; (5)without any sign of temporomandibular dysfunction.

InCoris TZl(ZIR), Celtra Duo(CD), IPS e.max(EMA), UPCERA LICI (LC), Vita enamic(ENA), UPCERA RUNCi (RC) were used to produce crowns for everyone by CEREC chairside CAD/CAM system. The milling trueness, postprocessing trueness and clinical adjustment of occlusal contact were quantitatively analyzed by the ATOS high-precision scanner and Geomagic reverse engineering software.

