## **Statistical Analysis Plan**

Statistical analysis will perform using SPSS software (SPSS version 26.0; SPSS) at a significance level of  $p=0.05$ . Descriptive statistics will perform first to obtain an overview of the data. A one-way analysis of variance (ANOVA)with randomized block design will perform to determine the significant differences on the milling trueness, postprocessing trueness and clinical adjustment of occlusal contact. Six groups will then be subsequently analyzed with the Bonferroni post hoc test. PASS 15.0 software (NCSS LLC, USA) will be used for the power test.

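### Do the eligibility criteria rule out every participant, because the study molar itself is a damaged tooth?

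*Combined protocol and SAP*

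**What the plan says.** The Study protocol section plans for ten participants: "Ten individuals (aged 20–30) will be selected to participate in the study". It introduces five numbered criteria with "The selection criteria for the participants are as follows", so they apply to the person and must all be met.

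- Criterion (1) defines the study tooth: "with one mandibular first molar requiring crown restoration that have undergone root canal treatment".
- Criterion (2) asks for a full adult set of teeth.
- Criterion (3) asks that participants be "without carious lesions, abrasions, attrition, erosions or any kind of tooth defects".
- Criterion (4) asks that they be "without any kind of restorations in occlusal surfaces".
- Criterion (5) excludes signs of jaw-joint dysfunction.

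Neither (3) nor (4) names the teeth it covers, and neither exempts the molar in (1). The Statistical Analysis Plan section does not discuss eligibility. The Study protocol section also says that crowns in all six materials are made for every participant, and the Statistical Analysis Plan section specifies an ANOVA with a randomised block structure.

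**The concern.** A molar that has had root canal treatment and now needs a crown is a tooth with a defect. If its opening has been filled, it may also carry an occlusal restoration. Criteria (3) and (4) exclude people with either, in the widest terms. Taken literally, meeting (1) means failing (3) or (4), so the eligible population is empty and each of the ten enrolments is a protocol deviation.

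If the literal reading is abandoned, the scope of (3) and (4) has to be inferred. That could matter for one of the three outcomes, the occlusal adjustment made in the clinic. Worn or restored opposing teeth could alter the contacts being adjusted. If screeners applied different scopes, the ten participants might not form a consistently defined group.

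**Working it through.** The plan gives no figure to reproduce here, and no sample size, power or error rate enters the argument. The check is one of logic, with a short look at the analysis model.

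**Step 1: is there a literal conflict?** A participant must satisfy (1), (3) and (4) together.

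- Criterion (1) against (3): needing a crown after root canal treatment implies lost tooth structure. If that counts as a defect under (3), the two conflict. This is the firmer of the two conflicts. It is not airtight, because the phrase about defects closes a list of decay and wear lesions and could be read in that narrower sense.
- Criterion (1) against (4): this depends on the state of the access opening. If filled, it is an occlusal restoration and (4) fails. If unfilled, it is a defect and (3) fails. That the opening runs through the occlusal surface is general dental knowledge and is not stated in the documents.

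The literal set is therefore empty: 0 of 10. What has been shown is a breach of (3) or (4), not necessarily of both.

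**Step 2: can the intended scope be recovered?** Compare the possible readings.

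| Reading of (3) and (4) | Can (1), (3) and (4) be met together? | Departure from the text |
|---|---|---|
| Every tooth, including the study molar | No | None |
| Every tooth except the study molar | Yes | Exempts only the tooth that (1) itself requires |
| Only opposing and adjacent teeth | Yes | Also exempts all distant teeth, which no criterion suggests |
| Only teeth in contact with the crown | Yes | Exempts still more teeth, which no criterion suggests |

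The second row is the minimal repair. It follows the ordinary rule that a specific requirement takes its object out of a general one. It also fits (2) and (5), which describe the mouth and jaw as a whole. The last two rows need limits that the text does not contain and that its wide wording points away from.

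**Step 3: does the recovered scope deal with the worry about opposing teeth?** Yes. With only the study molar exempt, (3) and (4) still cover every other tooth, including the opposing and adjacent ones.

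**Step 4: what if a screener were looser than that?** Every participant receives crowns in all six materials. I take the participant to be the block, which the design implies but the document does not say outright. For participant *i* and material *j*, the block model is

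y(i,j) = mean + participant(i) + material(j) + error(i,j).

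The difference between materials *j* and *k* within participant *i* is

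y(i,j) − y(i,k) = material(j) − material(k) + error(i,j) − error(i,k).

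The participant term cancels. A person's opposing dentition is common to all six of that person's crowns, so any additive effect it has drops out of the material comparison. Only a participant-by-material interaction would remain. The other two outcomes, trueness after milling and after post-processing, are properties of the crown, and no route from the scope of (3) and (4) to them has been suggested.

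**The case for a change.** The strongest opposing case accepts that the study molar is meant to be exempt and says this still leaves the scope open. Someone with a small filling in a distant tooth fails if all other teeth are covered, and passes if only the neighbouring and opposing teeth are. Two screeners could then disagree about the same person. With ten participants, a few such decisions would alter who is studied. The block structure removes a shift common to all six crowns, but not an effect that differs by material, and it does not fix the absolute size of the adjustments. The remedy costs only a few words.

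Parts of this stand. The text contains no exemption, and blocking does not remove an interaction. Average adjustment sizes do depend on whose mouths are studied. But the disagreement between screeners arises only if one of them adopts a limit that is nowhere in the text, and the wording of (3) and (4) tells against that. No particular interaction is argued for. A low cost of amendment is not a gain in itself: the added words would record the reading that investigators would already use.

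**Conclusion.** The criteria conflict if read word for word, but the slip is clerical and no change to the plan follows. The count of 0 eligible out of 10 restates the literal reading. It does not predict recruitment and does not establish ten deviations. Read as any investigator would read them, (3) and (4) cover all teeth other than the molar named in (1), and the list then works. No effect has been shown on the ten participants to be enrolled, the three outcomes, or the comparison of the six materials.

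This conclusion rests on three assumptions: that the specific criterion (1) takes its tooth out of the general criteria, that screeners add no narrower limit of their own, and that the participant is the block in the ANOVA. If the second failed, the outcome exposed would be occlusal adjustment. Its comparison between materials would be affected only if the state of the opposing teeth acted differently on different materials.

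### Does the unstated order of the six crowns within each participant undermine the planned randomised-block ANOVA?

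*Combined protocol and SAP*

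**What the plan says.** The Study protocol sets the sample: "Ten individuals (aged 20–30) will be selected to participate in the study". Criterion 1 admits people "with one mandibular first molar requiring crown restoration that have undergone root canal treatment". On production it lists six materials that "were used to produce crowns for everyone by CEREC chairside CAD/CAM system". It lists three outcomes: "The milling trueness, postprocessing trueness and clinical adjustment of occlusal contact were quantitatively analyzed".

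The Statistical Analysis Plan gives the model: "A one-way analysis of variance (ANOVA)with randomized block design will perform to determine the significant differences". A Bonferroni post hoc test on the six groups follows.

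The word 'randomized' occurs only in the name of that ANOVA. Neither section mentions a sequence, counterbalancing, or an order of milling, postprocessing or try-in.

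**The concern.** Every participant receives all six materials, so material is not allocated between people. In a randomised block design the thing left to randomise is the order of the six crowns inside each block. On the natural reading, six crowns are adjusted on one molar. That cannot be done simultaneously, so each crown has a position in a sequence.

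The text could be followed to the letter with the same sequence for all ten participants. Position would then be completely aliased with material. Any trend along the sequence that is common to all participants would appear as a material difference. The participant term cannot absorb it, because the trend lies within participants, and the Bonferroni correction does not address bias. Adding participants would make a false positive more likely. A reader might therefore ask whether the word 'randomized' is earned.

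**Working it through.** The plan gives no effect size, SD or power figure, so there is no stated number to reproduce. The check asks how much the missing order could matter.

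**Inputs from the documents.** 10 participants (blocks) and 6 materials (Study protocol); significance level 0.05 and Bonferroni post hoc test (Statistical Analysis Plan).

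**Inputs assumed.** One crown of each material per participant; independent normal errors with equal variance; no true material difference; a linear drift of d residual SD per position. The documents give no drift, so a range is shown.

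**Layout.** 10 × 6 = 60 crowns per outcome. Degrees of freedom: 6 − 1 = 5 for material and (10 − 1)(6 − 1) = 45 for error; critical F = 2.42. All pairs: 6 × 5 / 2 = 15, so 0.05 / 15 = 0.0033 per comparison.

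**One common order.** Centred positions are −2.5, −1.5, −0.5, 0.5, 1.5, 2.5, with sum of squares 2 × (6.25 + 2.25 + 0.25) = 17.5. The noncentrality is λ = 10 × 17.5 × d² = 175d². The rejection rate is the upper tail of the noncentral F(5, 45, λ) beyond 2.42. The first-versus-last bias is 5d.

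| d (SD per position) | First-to-last bias (SD) | λ | Omnibus rejection, common order | Any of 15 Bonferroni pairs, common order | Omnibus rejection, random order |
|---|---|---|---|---|---|
| 0.02 | 0.10 | 0.07 | 5.3% | about 4% | 5.0% |
| 0.05 | 0.25 | 0.4375 | 6.8% | about 5% | 5.0% |
| 0.1 | 0.5 | 1.75 | 13.0% | about 10% | 4.85% |
| 0.2 | 1.0 | 7.0 | 44.7% | about 36% | 4.95% |
| 0.3 | 1.5 | 15.75 | 83.7% | about 75% | 4.96% |

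The pairwise column comes from 100,000 simulated null trials per drift; without drift it is 3.6%. The last column uses a random permutation per participant and no position term in the model: 100,000 simulated trials for the first two rows, 20,000 for the rest. Simulating the common order with 20,000 trials gave 12.8%, 44.2% and 83.7% at d = 0.1, 0.2 and 0.3, in line with the noncentral F.

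**What random order costs if drift exists.** Drift moves into the error term, and residual SD grows by the factor √(1 + 3.5d²), where 3.5 = 17.5 / 5. This is 1.7%, 6.8% and 14.7% at d = 0.1, 0.2 and 0.3.

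**Reading the sections together.** In the Statistical Analysis Plan the phrase "with randomized block design will perform to determine the significant differences" belongs to the name of the model, and an ANOVA with participant as block is conventionally called by that name. If the phrase means more than that, it implies random order within block, and order then does not bias the comparison. On neither reading does it contradict the Study protocol.

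**By outcome.** Successive work on one tooth concerns only the clinical adjustment of occlusal contact. Milling and postprocessing trueness are assessed by scanner and software and do not depend on try-in order. Milling could be exposed through tool wear, but the documents do not say how many milling units are used or in what order.

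**The case for a change.** The best case for a change is that sequence is a core element of any within-participant comparison. This text permits the one arrangement that would make the comparison uninterpretable, and a computer-generated list with recorded positions would close the gap without more participants and without touching the ANOVA. If the crowns had already been made, as the past tense in the Study protocol might suggest, stating the order used would cost less still.

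Much of this stands. The omission is real, the arithmetic is right, and neither the block term nor the multiplicity correction would rescue a common order. What does not stand is the step from silence to fault. The documents do not say that a common order is used, and they give no drift. The large error rates follow from chosen inputs, and small drift does almost nothing. That six crowns are tried in on one molar is itself an inference: natural, and consistent with the block analysis, but the number of crowns per participant is not written down. Nor is randomising free: it could rule out milling in batches by material, and it moves any drift into the error term. The protocol is two short paragraphs that leave most procedures undescribed, and this is one of them.

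**Conclusion.** The plan does not need to change on this point. Nothing it states yields a wrong result. The analysis suits a complete 10 × 6 layout, and order biases it only if a common sequence and a shared drift of roughly 0.1 residual SD per position or more occur together. In that case the omnibus error rate would be 13% or higher; below 0.05 SD per position it stays under 7%, and with an order randomised per participant it stays at about 5%.

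The exposure is mainly in occlusal adjustment, possibly in milling. How the crowns were ordered is a detail that the investigators can settle in conduct and describe when they report, and a careful analyst would read the material differences with it in mind.

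This conclusion rests on reading the design as one crown per material per participant. It concerns order effects only: random order would not establish the other ANOVA assumptions, such as equal variance across six different materials.

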## **Statistical Analysis Plan**

Statistical analysis will perform using SPSS software (SPSS version 26.0; SPSS) at a significance level of  $p=0.05$ . Descriptive statistics will perform first to obtain an overview of the data. A one-way analysis of variance (ANOVA)with randomized block design will perform to determine the significant differences on the milling trueness, postprocessing trueness and clinical adjustment of occlusal contact. Six groups will then be subsequently analyzed with the Bonferroni post hoc test. PASS 15.0 software (NCSS LLC, USA) will be used for the power test.

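### Does naming the test both a one-way ANOVA and a randomized block design put the wrong error term in the plan?

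*Combined protocol and SAP*

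**What the plan says.** The study protocol section sets the layout. "Ten individuals (aged 20–30) will be selected to participate in the study", and the six listed materials "were used to produce crowns for everyone by CEREC chairside CAD/CAM system". That is 10 × 6 = 60 crowns, with each participant contributing one complete set.

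The Statistical Analysis Plan gives the test in one sentence: "A one-way analysis of variance (ANOVA)with randomized block design will perform to determine the significant differences". It applies this to three outcomes, "the milling trueness, postprocessing trueness and clinical adjustment of occlusal contact", and labels none of them primary. The follow-up is also brief: "Six groups will then be subsequently analyzed with the Bonferroni post hoc test". The plan does not name the block factor, write out the model or state the error term. It names SPSS as the package but no procedure within it.

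**The concern.** Read strictly, a one-way ANOVA has a single factor. Applied here, it would treat the 60 crowns as six independent groups of ten and ignore that each set of six was made for the same tooth. A randomized block analysis has two terms, material and participant. The two analyses give different F tests and different standard errors for the Bonferroni comparisons, so two analysts taking different halves of the phrase could report different p-values.

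The stake would be precision. Preparation and bite differ between participants, so crowns for one participant may well be correlated. Leaving that variation in the error widens intervals and hides real differences between materials. With ten participants and 15 pairwise comparisons, there is little precision to spare.

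A second worry applies even under the block reading. One pooled error serves all 15 pairs, which is exact only if the six materials have similar residual variance.

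**Working it through.** The plan states no power, effect size, SD or correlation, so there is no figure of its own to reproduce.

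**Inputs from the documents:** 10 participants, 6 materials, significance level 0.05, Bonferroni over 6 × 5 / 2 = 15 pairs (0.05 / 15 = 0.0033 per pair).

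**Assumption:** within-participant correlation (ICC) from 0 to 0.7.

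**Degrees of freedom.** One-way error: 6 × (10 − 1) = 54. Block error: (6 − 1) × (10 − 1) = 45. Critical F is 2.386 and 2.422; Bonferroni critical t is 3.071 and 3.100.

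**Error variance.** Set the total variance to 1, with participant variance ICC and residual variance 1 − ICC. The block error mean square has expectation 1 − ICC. The one-way error pools the participant and residual sums of squares, so its expectation is

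[9 × (6·ICC + 1 − ICC) + 45 × (1 − ICC)] / 54 = 1.

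The ratio of interval widths, one-way to block, is therefore about (3.071 / 3.100) / √(1 − ICC). At ICC 0.5 this is 0.991 / 0.707 = 1.40.

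**Power and type I error.** Simulation used 40,000 data sets per ICC under an additive normal model. The effect was set so that the block analysis has 80% power; equally spaced material means were used for the omnibus test.

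| ICC | Interval width ratio | One-way power, one pair | One-way power, omnibus | One-way omnibus type I error |
|---|---|---|---|---|
| 0 | 0.99 | 81% | 81% | 0.048 |
| 0.2 | 1.11 | 70% | 68% | 0.020 |
| 0.3 | 1.18 | 62% | 57% | 0.011 |
| 0.5 | 1.40 | 39% | 33% | 0.003 |
| 0.7 | 1.81 | 13% | 9% | below 0.001 |

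Omnibus power falls to half of 80% between ICC 0.4 (46%) and ICC 0.5 (33%). For a fixed large effect the loss is smaller: at f = 0.5 and ICC 0.5, one-way power is 80% against 99%.

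**Which analysis the text describes.** The SAP sentence contains the words for a block design. The study protocol supplies complete sets of six crowns per participant, and no other grouping in the documents could serve as the block. Read together, the two sections describe one treatment factor (material) with participant as block, tested on 5 and 45 df. A material-only analysis does not carry out the sentence as written.

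**Pooled error.** Suppose two of six materials had twice the residual SD (a scenario not drawn from the documents). The pooled variance is (4 × 1 + 2 × 4) / 6 = 2. For the one pair with both SDs doubled, the true standard error is √(4 / 2) = 1.41 times the pooled one; for a pair of low-variance materials it is √(1 / 2) = 0.71 times. Over 60,000 simulated data sets, the error rate is about 0.036 for the single high-variance pair, 0.009 for the eight mixed pairs and 0.0001 for the six low-variance pairs, against a nominal 0.0033. The family-wise rate over all 15 pairs is about 0.065, and the omnibus rate about 0.072.

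**The case for a change.** The best case for acting is that a SAP should leave one analysis, not two. This sentence governs all three outcomes, no other sentence corrects a misreading, and an analyst who looks up the words one-way ANOVA and Bonferroni could drop the participant term unnoticed. Writing out the model would take one sentence and cost almost nothing: critical t of 3.10 instead of 3.07, and under one percentage point of power at ICC 0.

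Parts of this stand. The wording is loose, the two error terms do differ, and the arithmetic on power is right. But the harm requires the analyst to disregard the design that the same sentence names, and the extra sentence would only restate that design. The size of the harm also rests on a correlation that the documents do not give and that need not be the same for all three outcomes. Bite and preparation are a plausible source of correlation for occlusal adjustment; nothing in the documents shows a large participant effect on milling trueness.

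On unequal variances, the worst single pair looks poor, but the family-wise rate that Bonferroni is meant to control rises only to about 0.065 in a fairly severe scenario. Switching to material-specific variances if the residual SDs differ would add a data-dependent choice without a stated trigger, and would estimate six variances from ten blocks. That is a trade-off, not a clear gain.

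**Conclusion.** No change follows. The phrase is imprecise, but its natural reading is the randomized block analysis with participant as block, which matches the study layout and gives a valid test on 5 and 45 df with the 15 comparisons on the same residual error. The unstated block factor and error term are details that the documents let an analyst fill in.

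The power loss is real only if the block is dropped. It is nil at ICC 0, moderate at 0.2 to 0.3, and about half at ICC near 0.5 when block power is 80%. These figures assume an additive normal model with equal residual variances and an ICC range chosen for illustration. Even in that case the error is on the conservative side: type I error falls below 0.05, so differences could be missed but none would be manufactured. The pooled-error point depends on unequal variances that the documents do not report, and is a fair trade-off at this sample size.

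### The Bonferroni post hoc test on the six materials is valid but needlessly conservative; Holm step-down keeps the same 5% bound within each outcome and loses no rejection

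*Combined protocol and SAP*

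**What the plan says.** The Study protocol section plans a small complete-block design. "Ten individuals (aged 20–30) will be selected to participate in the study", and six materials "were used to produce crowns for everyone by CEREC chairside CAD/CAM system". Each participant is therefore a block containing all six materials.

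The Statistical Analysis Plan sets a 0.05 significance level and specifies a randomised-block ANOVA "to determine the significant differences on the milling trueness, postprocessing trueness and clinical adjustment of occlusal contact". The follow-up is one sentence: "Six groups will then be subsequently analyzed with the Bonferroni post hoc test". The plan does not list the comparisons or name a step-down method. On power it says only "PASS 15.0 software (NCSS LLC, USA) will be used for the power test", with no SD, effect size or target power.

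**The concern.** Single-step Bonferroni holds all 15 pairs to the strictest threshold, 0.05/15, however many pairs have already been rejected. Once some hypotheses have been rejected, fewer can still be true nulls, and the remaining pairs can be tested at a larger level without breaking the 5% bound. Bonferroni does not use this room.

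With ten participants, pairwise power is limited unless the materials differ by well over one within-participant SD. At stake is whether some real differences between materials go undeclared that the same data and the same error bound would have supported. No false claim is at stake, because the planned test protects against false pairs within an outcome.

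**Working it through.** **Inputs from the documents.** Ten participants and six materials, all made for every participant (Study protocol); level 0.05, block ANOVA and Bonferroni follow-up (Statistical Analysis Plan). The plan gives no power figure to reproduce.

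**Assumptions.** All pairwise comparisons are intended, tests are two-sided, there is one crown per material per participant, errors are normal with equal variance, and pairwise tests use the pooled block-model error. Means are in units of the within-participant SD.

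**Step 1: family and degrees of freedom.** Pairs per outcome: 6 × 5 / 2 = 15. Error df: (6 − 1) × (10 − 1) = 45.

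**Step 2: Bonferroni.** Per-pair level 0.05/15 = 0.00333, critical |t| = 3.100 on 45 df. The levels sum to 15 × 0.00333 = 0.05, so the test is valid within an outcome.

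**Step 3: Holm.** Order the 15 p-values and compare them in turn with 0.05/15, 0.05/14, 0.05/13, …, 0.05/1, that is 0.00333, 0.00357, 0.00385, …, 0.05, stopping at the first failure. The first threshold equals Bonferroni's and all later ones are larger. Holm therefore rejects every pair that Bonferroni rejects and may reject more. Its 5% bound holds under any dependence between the pairs, given valid p-values. None of this depends on assumed effects.

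**Step 4: size of the gain.** Simulated average power per truly different pair in one outcome (100,000 runs per profile), with Tukey (critical |t| = 2.976) alongside:

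| Assumed means (SD units) | Bonferroni % | Holm % | Holm gain (points) | Tukey % |
|---|---|---|---|---|
| 0, 0, 0, 0, 0, 1 | 21.0 | 22.0 | 1.0 | 24.5 |
| 0, 0, 0, 1, 1, 1 | 20.9 | 22.7 | 1.8 | 24.4 |
| 0, 0.4, 0.8, 1.2, 1.6, 2 | 25.7 | 27.8 | 2.1 | 28.0 |
| 0, 0.5, 1, 1.5, 2, 2.5 | 37.4 | 40.8 | 3.4 | 39.8 |
| 0, 0, 1, 1, 2, 2 | 44.3 | 48.2 | 3.9 | 47.2 |
| 0, 0, 0, 0, 0, 1.5 | 60.2 | 62.4 | 2.2 | 64.6 |
| 0, 0, 0, 1.5, 1.5, 1.5 | 60.2 | 65.5 | 5.3 | 64.7 |
| 0, 0, 1.5, 1.5, 3, 3 | 73.5 | 81.4 | 7.9 | 76.5 |

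For smaller effects the gain nearly vanishes: 3.1 to 3.2% with one material shifted 0.5 SD, and 4.5 to 4.8% with equal steps of 0.2 SD. With very large separations power is already 100% and there is nothing to gain. No Bonferroni rejection was lost under Holm in any run.

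**Step 5: error within an outcome.** If no material differs, the chance of any false pair is about 3.7% under both methods. If some materials differ and others do not, Holm's realised rate is higher: at (0, 0, 5, 5, 10, 10) it is 4.8%, against 1.0% for Bonferroni. Both stay below 5%.

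**Step 6: Tukey.** Over Bonferroni, Tukey gains from 28.0 − 25.7 = 2.3 points to 64.7 − 60.2 = 4.5 points. It beats Holm in four of the eight profiles, including all three with power below 30%, and trails in the other four.

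**The case against.** The strongest reply is that nothing is wrong. Bonferroni is a recognised correction for six groups, it comes with matching intervals, and the named software produces it directly. That stands, and it limits this point to an optional improvement.

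The gain is also smallest where power is most needed. Where Bonferroni power is below 30%, Holm adds only about 2 points or less; the 7.9 comes from one profile spanning 3 SD. That stands too. With no SD or effect size in the documents, no figure in the table can be tied to this trial.

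One may ask why Holm rather than Tukey. Under equal variances there is no clear winner, so Tukey is an equal option.

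Holm also needs valid p-values. If one material has twice the SD of the others, pooled-error Bonferroni and Holm both give a 6.5% false-pair rate when no material differs; at (0, 0, 0, 3, 3, 3) the rates are 3.9% and 7.2%. With p-values from paired differences Holm stayed at or below 4.6% in all settings run, but power is lower: at (0, 0, 0, 1.5, 1.5, 1.5) it is 36.5% for Bonferroni and 41.3% for Holm.

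A reader might infer that Bonferroni is a mistake here, or that testing three outcomes at 0.05 inflates the study's error. The documents support neither. Bonferroni controls the error it is meant to control. The plan makes no claim that rests on whichever of the three outcomes is significant, and 5% holds for each taken as its own question.

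**Conclusion.** The point holds as a low-priority efficiency improvement. That Holm retains every Bonferroni rejection and the same 5% upper bound within each outcome follows from its thresholds, provided the pairwise p-values are valid. The same bound does not mean the same realised rate, which can rise from about 1% to nearly 5%.

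The size of the gain rests on assumed means, ten complete blocks, equal variances and the 15-pair reading. Under those assumptions it runs from about 0.1 point for a 0.5 SD shift, through 1 to 2 points where power is 20 to 26%, to 2 to 8 points where power is 37 to 74%. Requiring a significant ANOVA first, as the plan's wording may imply, changed power by at most 0.4 points and left the gain intact. Keeping Bonferroni for its simple matching intervals would be a reasonable decision.

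**What to change.** In the Statistical Analysis Plan, replace the Bonferroni post hoc sentence with wording such as: For each outcome, the 15 pairwise comparisons of the six materials form one family; two-sided unadjusted p-values from the block model will be adjusted by Holm's step-down method at a family-wise level of 0.05. If intervals that match the decisions matter more, name Tukey's test instead, accepting that it relies on the pooled variance.

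The change needs no extra participant or measurement. It has three costs:

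- Bonferroni intervals may not agree with every Holm decision.
- Holm must be computed from the unadjusted p-values, outside the SPSS Bonferroni option.
- The realised false-pair rate can rise within the 5% bound.

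The choice must be fixed before results are seen. The Study protocol describes production and measurement in the past tense ("The milling trueness, postprocessing trueness and clinical adjustment of occlusal contact were quantitatively analyzed by the ATOS high-precision scanner"), while the Statistical Analysis Plan is in the future tense, so the timing is unclear. If results are already known, either keep Bonferroni as the planned analysis or label the Holm results post hoc.

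### Does the unspecified PASS power test, with no planned intervals for material differences, need a change to the SAP?

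*Combined protocol and SAP*

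**What the plan says.** The Study protocol section sets the sample size in one sentence, "Ten individuals (aged 20–30) will be selected to participate in the study", and gives no reason for the number. It lists six materials that "were used to produce crowns for everyone by CEREC chairside CAD/CAM system", so each participant contributes one crown per material.

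The Statistical Analysis Plan section is one short paragraph. It plans descriptive statistics, then a block ANOVA at the 0.05 level on three outcomes ("milling trueness, postprocessing trueness and clinical adjustment of occlusal contact"), then pairwise follow-up: "Six groups will then be subsequently analyzed with the Bonferroni post hoc test". Power appears only in the closing sentence, "PASS 15.0 software (NCSS LLC, USA) will be used for the power test". None of the three outcomes is named as primary or tied to that sentence. No effect size, SD, within-participant correlation or target power is given, and confidence intervals are not mentioned.

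**The concern.** The sentence on power names software and nothing else. It comes last, after the ANOVA and the post hoc test, in a document that has already set the sample at ten. That order invites the reading that power will be calculated after the data are in, from the observed means and SD.

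Power calculated that way is uninformative. With the degrees of freedom and alpha fixed, it is a transformation of the p-value, so a non-significant result always comes with a low figure, and the figure cannot say which differences between materials the data exclude. Intervals for the pairwise differences would answer that question, and the SAP plans none. With 15 comparisons among six materials in ten participants, some non-significant pairs are likely unless differences are large. The worry is that a reader takes such pairs as evidence that the materials perform alike.

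**Working it through.** **The plan's own figure.** There is none to reproduce. Ten participants is stated without derivation, and no power value appears.

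**Inputs.** From the documents: 10 participants (blocks), 6 materials and alpha 0.05. Assumed: a complete 10 × 6 layout and two-sided pairwise tests. Treatment df = 6 − 1 = 5; error df = 9 × 5 = 45; pairs = 6 × 5 / 2 = 15. The documents give no SD, so differences are in units of the residual (within-block) SD.

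**Step 1: power from observed effects, block F test.** The critical value is F(0.95; 5, 45) = 2.422. Observed power is the probability that a noncentral F(5,45), with noncentrality 5 × F observed, exceeds 2.422.

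| omnibus p | F observed | noncentrality | observed power |
|---|---|---|---|
| 0.01 | 3.454 | 17.27 | 87% |
| 0.0238 | 2.895 | 14.48 | 80% |
| 0.05 | 2.422 | 12.11 | 71% |
| 0.10 | 1.980 | 9.90 | 61% |
| 0.20 | 1.529 | 7.64 | 49% |
| 0.50 | 0.883 | 4.42 | 29% |

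Under these conditions every non-significant omnibus result gives less than 71.3%, and the figure repeats p.

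**Step 2: the same power figure fits different data.** Take p = 0.20, F = 1.529. With d the largest pairwise difference, F = 10 × (sum of squared deviations of the six means) / 5.
- Two extreme means and four at the midpoint: the sum is d²/2, so F = d² and d = √1.529 = 1.236.
- Three high and three low: the sum is 6 × d²/4, so F = 3d² and d = √(1.529/3) = 0.714.

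The simultaneous Bonferroni half-width is t(1 − 0.05/30; 45) × √(2/10) = 3.100 × 0.447 = 1.386. The intervals are −0.15 to 2.62 and −0.67 to 2.10. Both go with 49% observed power.

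**Step 3: does the one-to-one mapping apply to this SAP?** It needs the residual SD and the block F test. The SAP names neither an SD nor a PASS procedure. Suppose the observed means and the total between-crown SD went into an ordinary one-way calculation, F(5,54), with critical value 2.386. Residual variance is (1 − ρ) times total variance, so the noncentrality at block p = 0.20 becomes 7.64 × (1 − ρ).

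| assumed ρ | noncentrality | power |
|---|---|---|
| 0 | 7.64 | 49% |
| 0.3 | 5.35 | 35% |
| 0.5 | 3.82 | 25% |
| 0.7 | 2.29 | 16% |

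So the link to p is exact in one case only. The other figures are no more useful for reading a null result.

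**Step 4: power on inputs chosen in advance.** At ten participants, with Bonferroni alpha 0.05/15 = 0.0033 per pair, a difference of 1.0 residual SD has 21% power and 1.5 has 60%; 80% is reached at 1.77. For the omnibus test, 80% needs noncentrality 14.48, or f = √(14.48/60) = 0.49. A run of this kind fits the SAP sentence as well as a run on observed effects.

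**The case for a change.** The case for requiring a change is that the ambiguity is itself a defect. As worded, PASS could be run after the data are seen, on any of three outcomes, with any inputs. Steps 1 and 2 show how little such a figure would convey. Step 4 shows that a true difference of one residual SD would be missed about 79% of the time after Bonferroni (100 − 21), so a reader of a null result needs intervals. The remedy would be a few words in the SAP and no more participants.

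Much of this stands. The missing details are real, and observed power would be a poor basis for interpreting a null result. Three points limit it.

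- The harm depends on a use the plan never proposes. The SAP does not say that observed effects are the inputs or that power will interpret non-significant results. Sentence order does not establish timing: a calculation done to support ten participants could be described in the same words.
- Silence on intervals does not exclude them. The paragraph does not list what will be reported, and intervals follow directly from the block model already planned.
- Whether 1.77 residual SD or f = 0.49 is large for these outcomes cannot be judged, because the documents give no SD and no difference of interest. The figures do not show that ten is too few.

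**Conclusion.** No change to the plan follows. The power sentence is incomplete but contains no wrong figure or rule, and the analyses that yield the study's findings, the block ANOVA and the Bonferroni comparisons, remain valid as written whatever is done with PASS. Specifying the power test or adding intervals would record practice the plan leaves unstated; it would not correct a result.

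The gap is one that a competent analyst closes in the ordinary course: run PASS on a difference and SD chosen in advance for a named outcome, and report the 15 pairwise differences per outcome with Bonferroni 95% intervals. Those would have a half-width of about 1.39 residual SD, or 1.39, 1.16, 0.98 and 0.76 total SD (1.386 × √(1 − ρ)) for assumed correlations of 0, 0.3, 0.5 and 0.7. If a report used observed power to explain a null result, that would be a fault of the report, which the SAP does not call for.

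The numbers rest on complete blocks, 45 error df, pooled residual variance and two-sided tests. The link between observed power and p (71% at p = 0.05) also requires the residual SD and the block F test.
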